2. To prospectively investigate the incidence of post-operative complications between the standard ERAS anesthesia protocol + active NSS-2 BRIDGE vs. ERAS anesthesia protocol + placebo (in-active) NSS-2 BRIDGE

3. To prospectively investigate role that the NSS-2 BRIDGE device may have in reducing opioid consumption after discharge and facilitating functional recovery

Study Design

The proposed pilot study will be conducted as a single-center prospective randomized double-blind, placebo-controlled trial at the University of Pittsburgh Medical Center (UPMC) Shadyside Hospital. Institutional review board approval will be obtained before eligible patients are recruited and consented. Trial will be registered at www.clinicaltrial.gov before beginning recruitment.

Recruitment

Potential subjects will be recruited in the pre-surgical clinic of [name] once they are scheduled for abdominal debulking surgery. Patients will be asked for their interest in pursuing a research study that involves wearing a percutaneous, auricular field stimulator for five days as a supplementary method of post-operative pain control. Patients who agree to participate in the trial will sign an IRB approved Informed Consent Form.

Randomization Process

Participating patients will be randomized by computer generated random numbers to either the control or intervention group.

Inclusion Criteria:

Over 18 years of age

Open abdominal debulking procedure as per our institution's Enhanced Recovery After Surgery (ERAS) anesthetic protocol.

Exclusion Criteria:

History of active depression, anxiety or catastrophizing

Active alcoholism or drug abuse

Severe chronic pain condition that requires daily preoperative opioid dependence

History of hemophilia

Patients with cardiac pacemakers

Patients with psoriasis vulgaris diagnosis

Treatment Groups

Control Arm: Control group will receive approved ERAS multimodal anesthesia protocol (Appendix 2) plus an inactive placebo NSS-2 BRIDGE device.

Interventional Arm: Intervention group will receive approved ERAS multimodal anesthesia protocol (Appendix 2) plus an active NSS-2 BRIDGE device

Data Collection and Outcome Measures

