Once patient has signed the Informed Consent to participate in this pilot study, demographic information and medical history will be collected from each participant on the day of surgery. The NSS-2 BRIDGE device will be applied to the ear by trained researcher in the immediate post-operative setting (PACU), as the research team has completed the necessary training required by the company to apply the device. Rescue analgesia will be permitted as per the approved ERAS multi-modal anesthetic protocol (Appendix 2), however, the patient will be made aware at the time of consent and throughout the trial that they can drop out of the study at any time if they do not like wearing the NSS- 2 BRIDGE device.

The patient will be assessed 12, 24, 48, 72, 96 and 120 hours post-operatively to collect total opioid consumption, incidence of adverse events, and level of comfort while wearing the NSS-2 BRIDGE device. When the patient is discharged from the hospital, they will be asked to complete a patient satisfaction survey. For patients discharged with the device attached, removal instructions and pre-paid return envelope will be given to patient to remove the device at 120 hours and send back to the hospital. The patient will be contacted 3 months post-operatively to again assess patient satisfaction with the pain management after surgery, and to assess functional recovery.

Pre-and-Post Metric Evaluation

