The use of a non-pharmacological NSS-2 BRIDGE has the possibility of providing analgesia to post-surgical patients and reducing the number of opioids required following abdominal surgery. This will significantly impact patient outcomes, as patients will experience fewer opioid-related side effects (such as respiratory depression, post-operative nausea and vomiting, constipation and delirium). This will also impact clinicians caring for post-operative patients, as there is the real potential they will have fewer conditions to monitor and treat as the patient recovers from surgery. The projected number of patients served by this project will initially be sixty enrolled participants at Shadyside Hospital, however, the data collected from this trial will serve countless patients and the community at large as physicians strive to move away from opioid use following surgery. Data collected from this pilot study will support a future proposal to the National Institute of Drug Abuse (NIDA) to fund a full-scale, randomized, placebo-controlled trial using the NSS-2 BRIDGE device.

Perhaps most importantly, the investigative use of the non-invasive NSS-2 BRIDGE device has the ability to significantly increase patient satisfaction in individuals who are opioid naïve or adverse to taking opioids as a method of pain control. Being able to offer the cancer patients at UPMC Shadyside such an alternative represents a great opportunity to increase patient satisfaction, outcomes and compliance as many patients increasingly fear the use of opioids. The NSS-2 BRIDGE will remain effective on the participant for five days, and will have lasting effects even after discharge from the hospital, which is a time when many patients turn to opioids to control pain. The way the efficacy of this device will be measured will be by comparing total perioperative opioid consumption between the intervention group (Standard of Care ERAS protocol + active NSS-2 BRIDGE) and control group (Standard of Care ERAS protocol + inactive NSS 2 BRIDGE), and total opioid consumption after discharge between the two groups. Other outcome measures include the incidence of respiratory depression, PONV, constipation and length of stay between the intervention and control groups.

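### Opioid consumption after discharge is a stated aim and efficacy comparison, but no listed contact collects it beyond 120 h

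*Protocol*

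**What the plan says.** **What is to be compared.** Aim 3 (Specific Aims) is to study the role of the device in "reducing opioid consumption after discharge and facilitating functional recovery". The Pre-and-Post Metric Evaluation section says how efficacy will be measured. The first comparison is described as "comparing total perioperative opioid consumption between the intervention group" and the control group; the second is "total opioid consumption after discharge between the two groups". The same section lists further outcomes, ending with "constipation and length of stay between the intervention and control groups".

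**What is to be collected.** The section Data Collection and Outcome Measures sets out the contacts:

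- Opioids: "The patient will be assessed 12, 24, 48, 72, 96 and 120 hours post-operatively to collect total opioid consumption", together with adverse events and comfort with the device.
- Discharge: "When the patient is discharged from the hospital, they will be asked to complete a patient satisfaction survey".
- Patients who go home wearing the device: instructions and a return envelope, "to remove the device at 120 hours and send back to the hospital".
- Three months: "The patient will be contacted 3 months post-operatively to again assess patient satisfaction with the pain management after surgery, and to assess functional recovery".

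No section mentions an opioid diary, a pill count, a prescription or refill record, or an opioid question after 120 h.

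**The concern.** The outcome is promised twice, once as an aim and once as a measure of efficacy, and the listed contacts do not deliver it. The gap lies in data collection, so it cannot be left to the statistical analysis plan. That plan can define windows and handle missing values, but it cannot analyse use that nobody asked about.

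The comparison matters to the trial's purpose. The protocol's rationale is opioid use and addiction after surgery. It expects the device's effect to last beyond discharge, and the results are meant to support a larger grant application. If the schedule is followed as written, the pilot will say little or nothing about opioid use at home. The fragment that might be captured runs over a different length of time for each patient.

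**Working it through.** The protocol gives no figure to reproduce here. The check sets the stated comparisons against the listed contacts and then works out how much time after discharge the schedule can cover.

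**Step 1. Match each outcome to a source.**

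| Stated outcome | Listed source |
|---|---|
| Perioperative opioid consumption | Six assessments, 12 to 120 h |
| Functional recovery (other half of Aim 3) | 3-month contact |
| Opioid consumption after discharge | None specific to it; only whatever part of the six assessments falls after discharge |

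The opioid assessments are at 12, 24, 48, 72, 96 and 120 h, which makes 6. Those later than 120 h number 0. The 3-month contact lists 2 items, and opioid use is neither of them.

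**Step 2. Post-discharge time covered.** Let L be the time from surgery to discharge in hours. The most that the schedule can capture after discharge is

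C = max(0, 120 − L).

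- If L ≥ 120, C = 0.
- If L < 120, C rises by one hour for each hour of shorter stay.

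The protocol foresees the second case, since it provides for patients who leave with the device attached. It does not say how the remaining assessments would be made at home, so C is an upper limit.

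**Step 3. Share of the follow-up.** The protocol gives no length of stay, so this step is illustrative. Assume that 3 months is 90 days and that discharge falls on day d. The share covered is at most max(0, 5 − d) / (90 − d).

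| Assumed discharge day | Days covered / days to the contact | Share |
|---|---|---|
| 2 | 3 / 88 | 3.4% |
| 3 | 2 / 87 | 2.3% |
| 4 | 1 / 86 | 1.2% |
| 5 or later | 0 | 0% |

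**Step 4. Comparability of the fragment.** Take two patients discharged 24 h apart, both before 120 h. Their counted home time differs by (120 − L₂) − (120 − L₁) = L₁ − L₂ = 24 h. If both use r mg per day at home, the earlier discharge shows r × 24/24 = r mg more, although the rate of use is the same. Length of stay is itself compared between the arms. If stay differed, the arm going home sooner would have more home hours counted, and raw totals would be shifted against it.

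**The case against.** The strongest reply is that silence is not exclusion. The data-collection text is two paragraphs in a funding request and is not exhaustive. Length of stay, for example, is a stated outcome that it does not list. The content of the satisfaction and functional-recovery instruments is not shown, and one of them could contain an opioid item. This stands to the extent that a reader should not infer that post-discharge opioid data will certainly be absent. The documents support only the statement that no listed contact collects them beyond 120 h. The reply does not close the gap, because length of stay can be read from the hospital record and opioid use at home cannot.

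A second reply concerns the unequal windows. Bias follows only if home use before 120 h is actually recorded, stay differs between arms, and raw totals are compared. No document gives a length of stay or a difference in it, and standardising to exposure time is an analysis choice. This stands: the argument is conditional and secondary to the missing source.

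A third reply is that asking for amounts at 3 months would not rescue the comparison, since recall of a total over that period is weak. This also stands, and it shapes the fix.

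**Conclusion.** The point holds as a mismatch within the protocol: a stated aim and a stated efficacy comparison have no matching data collection. Listed opioid assessments after 120 h number 0. Captured post-discharge time is at most max(0, 120 − L) hours, which is nil for anyone discharged at or after 120 h. The count and this bound follow from the schedule alone. The percentages of follow-up rest on assumed discharge days and a 90-day contact.

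Two stronger readings are tempting and are not supported. One is that the post-discharge comparison is already known to be biased by length of stay; that depends on conditions which the protocol does not establish. The other is that the opioid data to 120 h are at fault; nothing here touches their collection. The consequence is limited to the post-discharge comparison and the opioid part of Aim 3. It should be fixed before enrolment, because the data cannot be recovered well afterwards.

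**What to change.** 1. Add two opioid items to the existing 3-month contact, for all patients in both arms: any opioid use after discharge, and whether the patient is still using at the contact. The second needs no recall, and its timing is fixed from surgery, so it does not depend on length of stay.
2. Name these as the secondary post-discharge opioid outcome.
3. Keep total consumption after discharge only if the amount is recorded over a fixed number of days counted from discharge, the same in both arms, by a source nearer the time than the 3-month contact. A take-home tally or a prescription or refill record would serve, though the latter shows what was prescribed or dispensed, not what was taken.
4. If the amount will not be recorded in that way, delete the total-consumption comparison from the Pre-and-Post Metric Evaluation section and restate the opioid part of Aim 3 in terms of the items in step 1.

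Steps 1 and 2 cost a few self-reported questions at a contact already planned, plus protocol wording. Step 3 costs more, since it needs a new record for each patient. Step 4 costs a narrower stated outcome.

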Appendix 1: NSS- 2 BRIDGE device

Appendix 2: ERAS ANETHESIA PROTOCOL---SHADYSIDE HOSPITAL

1. Patients will undergo general anesthesia.

Encourage 1 month or more of abstinence from smoking and alcohol and 30 min walking/exercise every day leading up to surgery

Protein and carbohydrate rich diet for 1 week prior to surgery

Regular diet until midnight day before surgery, then clear liquids encouraged until arrival to hospital.

OSA screening

Pre-op multimodal analgesia ordered by surgeon to include oral Neurontin, Acetaminophen, and +/-Celebrex depending on case

PONV risk stratification

(PONV history, female, non-smoker, opiod/inhalation anesthetic use, emetogenic procedure 1 point each)

• Day of Surgery

DAS Nursing Staff: Heplock IV (KVO), DVT prophylaxis (SQ heparin), Bair Hugger

Pain Service: Avoid narcotics for block placement

- Continuous Quadratus Lumborum blocks for post op analgesia . Ropivicaine 0.5% 20 ml (single shot bilat)
- Decadron 4mg
- Dexmedetomidine (Precedex) 40 mcg
- 500 cc IV fluid bolus with block
- PONV prophylaxis, according to risk score (Attending Anesthesiologist order)
- Low: no prophylaxis
- Medium (1-2 risk factors): Scop patch or Perphenazine or Emend
- High (>2 risk factors): Emend and Scop patch
- Anesthesia
- Warm IV fluids, underbody warming blanket, and Bair Hugger

- Antibiotics per protocol according to procedure
- Induction (Guidelines only) Adjust doses as clinically relevant.
 Propofol (2 mg/kg), Ketamine (0.3 mg/kg), Precedex 0.3 mcg/kg, muscle relaxant, and NO OPIOIDS.
- Spinal
- Maintenance TIVA to include separate infusions of Propofol, Ketamine (0.2 mg/kg/hr), Precedex (0.2-0.8 mcg/kg/hr) titrated to effect. concentration is NOT in the Alaris library – must be programmed for 100 mg/100cc**
- **NO OPIOIDS**; avoid use of Nitrous Oxide
- Magnesium 2-4 gm IV
- Ketorlac 15 mg IV at end of case if approved by surgeon
- NO IV Acetaminophen (unless not given po pre-op)
- Ondonsatron 4 mg (save Haldol for rescue in PACU). There is NO need to give IV Decadron
- Tidal Volumes recommended at <6-8 cc/kg; PEEP 6-8, FiO2 <80%, recruit lungs
- Fluid Management via Goal Directed Therapy with SVV (Vigileo) if aline in place.
- Avoid NSS (PLtye preferred or LR if not available). Avoid replacement of fluid deficit. 8-10 cc/kg/hr + replacement of EBL as guideline. IVF not to exceed >2L above expected losses.
- Emergence Discontinue Ketamine/Precedex 45-60 min prior to emergence, then titrate Propofol to closure and emergence.

PACU

- Clear liquid intake to start ASAP in PACU; if aspiration risk, IVF maintenance at 75 cc/hr.
- Ketamine 30 mg PO

The postop orders in the surgeon's care plan include

Oral opiates, IV rescue opiates, acetaminophen, toradol, Celebrex,

The AIPPS orders should be only for

Ketamine infusion

Neurontin at bedtime

PCA if needed (goal is to not use PCA unless necessary such as chronic opiate users, big open cases, etc).

QL block

Age <60 Ropi 0.5% 20 mL, dexmedetomidine 30 mcg, dexamethasone 4 mg per side

Age >60 Ropi 0.5 % 20 mL, dexmedetomidine 20 mcg, dexamethasone 4 mg per side

Plus several hundred mL fluid bolus

Plus glycopyrrolate 0.2 mg IV

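### Appendix 2, which applies to both arms, doses the quadratus lumborum block twice, and the dexmedetomidine entries for patients under 60 cannot be reconciled

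*Protocol*

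**What the plan says.** The Treatment Groups section of the Protocol makes Appendix 2 part of each arm's regimen. For the active arm it reads "Intervention group will receive approved ERAS multimodal anesthesia protocol (Appendix 2) plus an active NSS-2 BRIDGE device", and the control arm is described in the same way with an inactive device.

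Appendix 2 then describes the QL block twice.

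- **Day of Surgery, Pain Service list.** The block bullet is "Continuous Quadratus Lumborum blocks for post op analgesia . Ropivicaine 0.5% 20 ml (single shot bilat". Below it come Decadron (dexamethasone) 4 mg, "Dexmedetomidine (Precedex) 40 mcg" and "500 cc IV fluid bolus with block". There is no age split, and neither additive is marked as a total or a per-side amount.
- **QL block list, at the end of the appendix.** This is split by age: "Age <60 Ropi 0.5% 20 mL, dexmedetomidine 30 mcg, dexamethasone 4 mg per side" and "Age >60 Ropi 0.5 % 20 mL, dexmedetomidine 20 mcg, dexamethasone 4 mg per side". It adds "Plus several hundred mL fluid bolus" and glycopyrrolate.

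No sentence links the two lists, says that one governs, or says that they describe different blocks.

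**The concern.** An anaesthetist who follows the first list gives every adult the same dexmedetomidine amount with the block. One who follows the second gives an amount that depends on age. The inclusion criteria admit adults over 18 with no upper limit, so patients in both age bands can be enrolled. If the two lists dose the same block, a patient under 60 would receive a different amount depending on which half of the appendix was read.

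What is at stake is dosing safety and a clear definition of background care. The block is given for postoperative analgesia in a trial whose primary endpoint is opioid consumption, so the protocol should state plainly what every patient receives. Both arms share the same text, so the inconsistency does not in itself favour either arm.

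**Working it through.** **Do the lists describe the same block?** Both give ropivacaine 0.5% 20 mL, dexamethasone 4 mg, dexmedetomidine and a fluid bolus. The first list ties its bolus to the block. The Anesthesia list that follows says "There is NO need to give IV Decadron", which fits dexamethasone having already been given with the block. The separate dexmedetomidine doses for induction and maintenance are not part of this comparison. The same-block reading is an inference, but the text supports it.

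**Inputs (Appendix 2).** Dexmedetomidine is 40 mcg in the Pain Service list. In the QL block list it is 30 mcg under 60 and 20 mcg over 60.

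**Ambiguities.** The 40 mcg may be the total for two sides (40) or per side (2 × 40 = 80). In the second list, the closing words per side may cover the whole line (2 × 30 = 60; 2 × 20 = 40) or only the dexamethasone (30; 20). Crossing these gives four readings.

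Gap = first-list bilateral total − second-list bilateral total. The percentage is the gap divided by the second-list total.

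| Reading of first list | Reading of second list | Under 60 (mcg) | Gap | Over 60 (mcg) | Gap |
|---|---|---|---|---|---|
| total | per side | 40 vs 60 | −20 (−33%) | 40 vs 40 | 0 |
| per side | per side | 80 vs 60 | +20 (+33%) | 80 vs 40 | +40 (+100%) |
| total | total | 40 vs 30 | +10 (+33%) | 40 vs 20 | +20 (+100%) |
| per side | total | 80 vs 30 | +50 (+167%) | 80 vs 20 | +60 (+300%) |

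Under 60, none of the four readings agrees. Over 60, one of four agrees: the first list as a two-side total and the second as per side.

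**Cross-check on dexamethasone.** The second list gives 4 mg per side, so 2 × 4 = 8 mg bilaterally. The first list's 4 mg matches only if it too is per side (2 × 4 = 8); read as a total it is 4 against 8 mg. The over-60 dexmedetomidine match needs the opposite reading of the adjacent line. No uniform reading of the first list therefore reconciles both additives, even over 60.

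**Ropivacaine and fluid.** A bilateral 20 mL can be read as 20 mL per side, and 500 cc is compatible with several hundred mL. I claim no discrepancy for either.

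**The case against.** The strongest reply is that the first list is a workflow checklist arranged by team and the second is the age-specific detail behind it. The over-60 match (2 × 20 = 40 mcg) fits that view, and the fault would then be a missing cross-reference rather than two rival regimens. This is plausible, but a summary should agree with its detail, and for patients under 60 it does not on any reading. The appendix does label some doses as guidelines to be adjusted, but that label is attached to Induction and not to either block list.

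Second, the upper end of the range is stretched. The 50 mcg gap requires an unlabelled first-list dose to be per side and the second list's closing words to cover only dexamethasone. That is fair: 20 mcg is the figure to carry, and the rest shows how ambiguous the labels are.

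Third, the block bullet uses both a continuous and a single-shot description. The second term may describe only the ropivacaine bolus, and line breaks may have been lost in the PDF text. The wording is worth clarifying, but the finding does not depend on it.

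Fourth, this is the hospital's approved standard care, given alike to both arms, and the trial does not test the block. That limits the statistical consequence. It does not remove a contradictory dose from a document that assigns this care to trial patients.

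**Conclusion.** The concern holds. If both lists dose the same block, the dexmedetomidine entries for patients under 60 conflict on all four readings. The gap is 20 mcg (33% of the QL block list figure) when that list is read as per side, and 10 to 50 mcg (33% to 167%) over all readings. Over 60, the dexmedetomidine entries agree on one reading only, and that reading puts dexamethasone out of agreement.

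The conclusion rests on the same-block inference. If two different blocks were intended, the appendix would still have to say so. The Protocol does not give the proportion of patients expected to be under 60, so the number affected cannot be stated. It also gives no standard deviation for opioid consumption, so any effect on the variability of the primary endpoint cannot be calculated, and none is claimed. The point should be corrected on grounds of dosing safety.

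**What to change.** The responsible anaesthesia team should reconcile the Pain Service and QL block lists in Appendix 2 into a single block specification. It should:

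- say which list governs, or state explicitly that the two describe different blocks;
- mark every dose as a bilateral total or per side;
- settle the continuous and single-shot wording in the block bullet;
- assign patients aged exactly 60, who fall in neither of the present bands;
- say whether glycopyrrolate, which appears only in the second list, belongs to the block regimen.

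No dose or technique is proposed here; those choices are for the clinical team.

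The cost is a text correction to Appendix 2. Because this is the hospital's own approved protocol, its anaesthesia team must agree the wording. Sample size, arms, assessments and data collection are unchanged.
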